### **3.5. Definition of End of Trial**

If the trial is not terminated for a reason provided in [Section 4.4.3](#), the end of the trial is defined as 24 months after the last subject has received the last planned dose of study drug.

### **3.6. Medical Care of Subjects After End of Trial**

At the end of the protocol-specified periods of active study therapy, the Sponsor will not continue to supply study drug to subjects/investigators unless the Sponsor chooses to extend the study. The investigator should ensure that the subject receives appropriate standard of care to treat the condition under study.

Upon withdrawal from trial treatment, subjects may receive the care upon which they and their physicians agree. Subjects will be followed for survival and AEs as specified in [Section 6](#).

## 4. SELECTION OF TRIAL POPULATION

### 4.1. Target Population

Phase 1 (Parts A1 and A2):

Male and female subjects over the age of 18 years with metastatic or locally advanced solid tumors for which no standard therapy is available or standard therapy has failed.

Phase 2:

Female subjects over the age of 18 years with recurrent and/or metastatic cervical cancer who have relapsed after a platinum-based treatment regimen for advanced (recurrent, unresectable, or metastatic) disease.

After the interim analyses, subsequent enrollment of subjects may be based on biomarker enrichment (including but not limited to PD-L1 expression). In such cases, tumor tissue must be positive for the selected entry biomarker prior to subject enrollment.

5. Have a life expectancy of at least 3 months and an Eastern Cooperative Oncology Group (ECOG) performance status of 0 or 1.
6. Have adequate organ function as indicated by the following laboratory values:
  - a. Adequate hematological function defined by absolute neutrophil count (ANC)  $\geq 1.5 \times 10^9/L$ , platelet count  $\geq 100 \times 10^9/L$ , and stable hemoglobin  $\geq 8 \text{ g/dL}$  (without transfusions within 1 week before first dose).
  - b. Adequate hepatic function based by a total bilirubin level  $\leq 1.5 \times$  the institutional upper limit of normal (IULN), aspartate aminotransferase (AST) level  $\leq 2.5 \times$  IULN, alanine aminotransferase (ALT) level  $\leq 2.5 \times$  IULN, and alkaline phosphatase  $\leq 2.5 \times$  IULN.
  - c. Adequate renal function defined as creatinine  $\leq 1.5 \times$  IULN **OR** calculated creatinine clearance  $\geq 50 \text{ mL/min}$  for subjects with creatinine levels  $> 1.5 \times$  IULN (if no local guideline is available, creatinine clearance should be calculated using the Cockcroft-Gault Method).
  - d. Adequate coagulation defined by international normalized ratio (INR) or prothrombin time  $\leq 1.5 \times$  IULN (unless the subject is receiving anticoagulant therapy); and activated partial thromboplastin time (aPTT)  $\leq 1.5 \times$  IULN (unless the subject is receiving anticoagulant therapy)
7. Other than the cancer for which the subject is enrolled, have no history of prior malignancy, with the exception of basal cell carcinoma of the skin, superficial bladder cancer, squamous-cell carcinoma of the skin, or has undergone potentially curative therapy with no evidence of that disease recurrence for 5 years since initiation of that therapy.
8. In Phase 2, subjects must provide a sufficient and adequate formalin-fixed paraffin embedded (FFPE) tumor tissue sample preferably from the most recent biopsy of a tumor lesion, collected either at the time of or after the diagnosis of advanced or metastatic disease has been made AND from a site not previously irradiated. If no tumor tissue is available, a fresh biopsy will be required. (See [Section 6.4.2.1](#) for details.)

**Note:** Tissue from needle or excisional biopsy or from resection is required.

9. Female subjects must have a negative serum pregnancy test at screening (within 72 hours before first dose of study drug) if of childbearing potential or be of non-child bearing potential. Non-childbearing potential is defined as (by other than medical reasons):
  - a.  $\geq 45$  years of age and has not menstruated for greater than 1 year,
  - b. Amenorrheic for  $< 2$  years without a hysterectomy and oophorectomy and a follicle-stimulating hormone (FSH) value in the postmenopausal range upon pretrial (screening) evaluation,
  - c. Whose status is post hysterectomy, oophorectomy or tubal ligation.
10. If of childbearing potential, female subjects must be willing to use 2 highly effective methods (defined in the informed consent form [ICF]) throughout the study, starting with the screening visit through 120 days after the last dose of study drug.  
**Note:** Abstinence is acceptable if this is the established and preferred contraception for the subject.
11. Male subjects with a female partner(s) of child-bearing potential must agree to use 2 highly effective methods (defined in the ICF) throughout the trial starting with the screening visit through 120 days after the last dose of study drug is received. Males with pregnant partners must agree to use a condom; no additional method of contraception is required for the pregnant partner.  
**Note:** Abstinence is acceptable if this is the established and preferred contraception for the subject.
12. Is willing and able to comply with the requirements of the protocol.

#### 4.3. Exclusion Criteria

The subject must be excluded from participating in the trial if the subject:

1. Is currently participating and receiving study therapy or has participated in a study of an investigational agent and received study therapy or used an investigation device within 4 weeks before the first dose of treatment.
2. Has an inadequate washout period prior to first dose of study drug defined as:
  - a. Received systemic cytotoxic chemotherapy or biological therapy within 3 weeks before first dose,
  - b. Received radiation therapy within 3 weeks before first dose, or
  - c. Had major surgery within 4 weeks before first dose.
3. Has received prior therapy with:
  - a. Any antibody/drug targeting T-cell co-regulatory proteins (immune checkpoints) such as anti-PD-1, anti-PD-L1, or anti-cytotoxic T-lymphocyte antigen 4 (CTLA-4) antibodies
  - b. For Phase 2:  $> 1$  systemic treatment regimen for the advanced (recurrent, unresectable, or metastatic) cervical cancer for which the subject is considered for the study

**Note:** In Phase 1, prior treatment with a CTLA-4 antibody is permissible for subjects with metastatic melanoma.

4. Has persisting toxicity related to prior therapy of NCI CTCAE Grade > 1 severity.

**Note:** Sensory neuropathy or alopecia of Grade  $\leq 2$  is acceptable.

5. Is expected to require any other form of systemic or localized antineoplastic therapy while on trial (including maintenance therapy with another agent, radiation therapy, and/or surgical resection).
6. Has known severe hypersensitivity reactions to fully human monoclonal antibodies (National Cancer Institute Common Terminology Criteria for Adverse Events version 4.03 [NCI CTCAE] Grade  $\geq 3$ ), any history of anaphylaxis, or uncontrolled asthma.
7. Is receiving systemic corticosteroid  $\leq 7$  days prior to the first dose of trial treatment or receiving any other form of systemic immunosuppressive medication (corticosteroid use on study for management of immune-related adverse events, and/or a premedication for IV contrast allergies/reactions is allowed). Subjects who are receiving daily corticosteroid replacement therapy are an exception to this rule. Examples of permitted therapy are daily prednisone at doses of 5 to 7.5 mg or equivalent hydrocortisone dose, and steroid therapy administered by topical, intraocular, intranasal, and/or inhalation routes.
8. Has a central nervous system (CNS) tumor, metastasis(es), and/or carcinomatous meningitis identified either on the baseline brain imaging obtained during the screening period OR identified prior to consent.

**Note:** Subjects with history of brain metastases that have been treated may participate provided they show evidence of stable supra-tentorial lesions at screening (based on 2 sets of brain images, performed  $\geq 4$  weeks apart, and obtained after the brain metastases treatment). In addition, any neurologic symptoms that developed either as a result of the brain metastases or their treatment must have resolved or be minimal and be expected as sequelae from treated lesions. For individuals who received steroids as part of brain metastases treatment, steroids must be discontinued  $\geq 7$  days prior to first dose of study drug.

9. Has active or history of autoimmune disease that has required systemic treatment within 2 years of the start of trial treatment (i.e., with use of disease modifying agents, corticosteroids or immunosuppressive drugs). Replacement therapy (i.e., thyroxine, insulin, or physiologic corticosteroid replacement therapy for adrenal or pituitary insufficiency, etc.) is not considered a form of systemic treatment.

**Note:** Subjects with diabetes type 1, vitiligo, psoriasis, hypo-, or hyperthyroid disease not requiring immunosuppressive treatment are eligible.

10. Has had an allogeneic tissue/solid organ transplant.
11. Has or had interstitial lung disease (ILD) OR has had a history of pneumonitis that has required oral or IV corticosteroids.
12. Has an active infection requiring intravenous systemic therapy.
13. Has known history of Human Immunodeficiency Virus (HIV) (HIV 1/2 antibodies).

14. Has known active Hepatitis B, Hepatitis C or tuberculosis. Active Hepatitis B is defined as a known positive HBsAg result. Active Hepatitis C is defined by a known positive Hep C Ab result and known quantitative HCV RNA results greater than the lower limits of detection of the assay.
15. Has clinically significant (i.e., active) cardiovascular disease: cerebral vascular accident/stroke or myocardial infarction within 6 months before enrollment, unstable angina, congestive heart failure (New York Heart Association class  $\geq$  II), or serious uncontrolled cardiac arrhythmia requiring medication.
16. Has a history or current evidence of any condition, therapy, or laboratory abnormality that might confound the results of the trial, interfere with the subject's participation for the full duration of the trial, or is not in the best interest of the subject to participate, in the opinion of the treating Investigator.
17. Has known psychiatric or substance abuse disorders that would interfere with cooperation with the requirements of the trial.
18. Is, at the time of signing informed consent, a regular user (including "recreational use") of any illicit drugs or had a recent history (within the last year) of substance abuse (including alcohol).
19. Is legally incapacitated or has limited legal capacity.
20. Is pregnant or breastfeeding or expecting to conceive or father children within the projected duration of the trial, starting with the screening visit through 120 days after the last dose of study drug.

#### **4.4. Criteria for Subject Withdrawal**

##### **4.4.1. Withdrawal from Treatment**

The subject must be withdrawn in the event of any of the following:

- Occurrence of an event that would have been considered an exclusion criterion prior to enrollment, that is clinically relevant and affects the subject's safety, and if discontinuation is considered necessary by the investigator and/or Sponsor.
- Radiological disease progression, defined by RECIST 1.1 as defined in [Section 6.4.4.3](#), unless the subject is considered to derive clinical benefit from the treatment by the investigator, is clinically stable and there is agreement with the Sponsor ([Section 5.4.5](#)).

Clinical stability is defined by:

- Absence of new symptoms and signs indicating clinically significant disease progression
- No decline in ECOG performance status.
- Absence of rapid progression of disease or progressive tumor at critical anatomical sites (e.g., cord compression) requiring urgent alternative medical intervention.

- Note: For Phase 2, tumor assessments should be performed every 6 weeks ( $\pm$  3 days) from first treatment dose until discontinuation of treatment, regardless of reason for discontinuation. This includes patients who are being treated past disease progression. Clinical disease progression, in the absence of radiologic progression on the basis of RECIST 1.1, including 1 or more of the following:
  - signs and/or symptoms of consistent with clinically significant progression of disease, including worsening of laboratory values, appearance of new lesion/worsening of the lesion best seen clinically, etc.
  - decline in ECOG performance status
  - tumor progression at critical anatomical sites that requires urgent medical intervention (e.g., CNS metastasis with potential for cord progression)
  - initiation of chronic opiates, or initiation of chemotherapy or new antineoplastic therapy, palliative radiation therapy, or surgery
- Any Grade 2 drug-related uveitis or eye pain or blurred vision that does not respond to topical therapy and does not improve to Grade 1 severity within 2 weeks OR requires systemic treatment;
- Any Grade  $\geq$  2 drug-related pneumonitis or interstitial lung disease that does not resolve to dose delay and systemic corticosteroids (also see Pulmonary Immune Related Adverse Event Management Algorithm [[Section 5.6.3](#)]);
- Any Grade 2 or 3 drug-related toxicity that does not resolve in  $\leq$  6 weeks;
- Any Grade 3 drug-related bronchospasm, hypersensitivity reaction, or infusion-related reaction, regardless of duration; with the exception of Grade 3 infusion-related reactions resolving within 6 hours and controlled with medical management;
- Any Grade 3 non-skin, drug-related AE lasting  $>$  7 days, with the following exceptions for uveitis, pneumonitis, bronchospasm, diarrhea, colitis, neurologic toxicity, hypersensitivity reactions, infusion reactions, endocrinopathies, and laboratory abnormalities:
  - Grade 3 drug-related uveitis, pneumonitis, bronchospasm, diarrhea, colitis, neurologic toxicity, hypersensitivity reaction, or infusion reaction of any duration requires discontinuation;
  - Grade 3 drug-related endocrinopathies adequately controlled with only physiologic hormone replacement do not require discontinuation;
  - Grade 3 drug-related laboratory abnormalities do not require treatment discontinuation except:
    - Grade 3 drug-related thrombocytopenia  $>$  7 days or associated with bleeding requires discontinuation;
    - Any drug-related liver function test (LFT) abnormality that meets the following criteria require discontinuation (also see hepatic immune-related AE management algorithm [[Table 7](#)]):

- ▶ AST or ALT  $> 8 \times$  ULN;
- ▶ Total bilirubin  $> 5 \times$  ULN;
- ▶ Concurrent AST or ALT  $> 3 \times$  ULN AND total bilirubin  $> 2 \times$  ULN;
- Any Grade 4 drug-related AE or laboratory abnormality, except for the following events, which do not require discontinuation:
  - Grade 4 neutropenia  $< 7$  days;
  - Grade 4 lymphopenia or leukopenia;
  - Isolated Grade 4 electrolyte imbalances/abnormalities that are not associated with clinical sequelae and are corrected with supplementation/appropriate management within 72 hours after their onset;
- Any AE, laboratory abnormality, or intercurrent illness which, in the judgment of the Investigator, presents a substantial clinical risk to the subject with continued treatment;
- Tumor flare phenomenon, defined as local pain, irritation, or rash localized at sites of known or suspected tumor does not require treatment discontinuation.
- Any requirement for  $\geq 10$  mg per day of prednisone (or equivalent) for  $> 6$  weeks;
- Any recurrence of a Grade 3 or 4 drug-related toxicity;
- Dose delay which results in no AGEN2034 dosing for more than 6 weeks.
- Occurrence of AEs, resulting in discontinuation of trial drug that is desired or considered necessary by the investigator and/or the subject (if applicable).
- Occurrence of pregnancy (if applicable).
- Use of a non-permitted concomitant drug, as defined in [Section 5.5.2](#), in which the predefined consequence is withdrawal from study drug (Sponsor may be contacted to discuss whether trial treatment must be discontinued).
- Noncompliance for non-medical reasons ([Section 6.4.1.11](#))

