**Table 2: Phase 1 Dosing Regimens**

Part and Agent	Dose	Schedule	Duration of Treatment
Part A1: Dose Level 1			
AGEN2034	1 mg/kg IV 	Every 2 weeks	Up to 24 months
Part A1: Dose Level 2			
AGEN2034	3 mg/kg IV 	Every 2 weeks	Up to 24 months
Part A1: Dose Level 3			
AGEN2034	10 mg/kg IV 	Every 2 weeks	Up to 24 months
Part A2: Dose Level 1			
AGEN2034	6 mg/kg IV 	Every 3 weeks	Up to 24 months
Part A2: Dose Level 2			
AGEN2034	10 mg/kg IV 	Every 3 weeks	Up to 24 months

 Infusion time is 60 minutes (-10/+20 min)

In Phase 2, all subjects will receive AGEN2034 at a dose of 3 mg/kg IV over 60 minutes (-10/+20 min) every 2 weeks for up to 24 months.

In both Phases, subjects will be treated for up to 24 months, regardless of dose delays, as long as the subject meets criteria to remain on therapy.

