## 5.5. Concomitant Treatments

### 5.5.1. Acceptable Concomitant Medications

All treatments that the investigator considers necessary for a subject's welfare may be administered at the discretion of the investigator in keeping with the community standards of medical care. All concomitant medication will be recorded on the eCRF including all prescription, over-the-counter (OTC), herbal supplements, and IV medications and fluids. If changes occur during the trial period, documentation of drug dosage, frequency, route, and date will also be included on the eCRF.

Palliative and supportive care is permitted during the course of the trial for underlying medical conditions and management of symptoms.

Surgery for tumor control or symptom management is not permitted during the study. Palliative radiotherapy is permitted to a single lesion if considered medically necessary by the treating physician as long as the lesion is NOT a RECIST 1.1-defined target lesion and treatment is NOT administered for tumor control. Trial therapy should be held during the course of palliative radiotherapy and should be resumed no earlier than the next scheduled administration of trial therapy. The specifics of the radiation treatment, including the location, will be recorded.

All concomitant medications received within 30 days before the first dose of trial treatment through the Safety Follow-up Visit should be recorded.

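### Section 4.4.1 forces withdrawal from treatment when palliative radiotherapy starts, while Section 5.5.1 permits it to a single non-target lesion with study drug held and then resumed

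*Protocol*

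**What the plan says.** Protocol 4.4.1 (Withdrawal from Treatment) opens with a mandatory instruction: the subject must come off treatment if any listed event occurs. One event is "Clinical disease progression, in the absence of radiologic progression on the basis of RECIST 1.1, including 1 or more of the following". The sub-items are clinically significant signs or symptoms, a fall in ECOG status, progression at a critical site needing urgent intervention, and "initiation of chronic opiates, or initiation of chemotherapy or new antineoplastic therapy, palliative radiation therapy, or surgery". The last is not limited by lesion, intent or reason and does not refer to 5.5.1.

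Protocol 5.5.1 (Acceptable Concomitant Medications) says: "Palliative radiotherapy is permitted to a single lesion if considered medically necessary by the treating physician". Two conditions follow: the lesion must not be a RECIST 1.1 target lesion, and the aim must not be tumor control. Study drug is held during the radiotherapy and restarted no earlier than the next scheduled dose.

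Among radiation treatments, Protocol 5.5.2 bars only radiation for tumor control during screening and treatment, which agrees with 5.5.1.

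**The concern.** The two sections give opposite instructions for the same subject. A site that irradiates within 5.5.1 and then restarts drug breaches a mandatory rule in 4.4.1. A site that applies 4.4.1 literally ends treatment permanently where 5.5.1 foresees only an interruption. With about 60 Phase 2 centers, different sites can reasonably act differently.

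The outcome is also perverse. A clinically stable subject with RECIST progression may stay on drug with Sponsor agreement (4.4.1 and 5.4.5), while a subject without RECIST progression who receives permitted symptom relief must stop. What is at stake is subject treatment and consistent conduct, not the primary analysis.

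**Working it through.** The documents state no figure to reproduce, so the main check is a comparison of text.

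**1. Is the 4.4.1 item sufficient alone?** Yes. The lead-in is mandatory for any listed event, and the clinical-progression event is met by one or more sub-items. Starting palliative radiation is therefore enough.

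**2. Does 5.5.1 cover the same act and give a different consequence?** Yes. Take a subject with no RECIST progression who has one painful non-target lesion irradiated for symptoms:

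| Section | Status of the radiotherapy | Consequence for study drug |
|---|---|---|
| 4.4.1 | Counts as clinical progression | Mandatory withdrawal |
| 5.5.1 | Permitted | Hold, then resume |
| 5.5.2 | Not prohibited (not for tumor control) | None stated |

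**3. Can an exemption be implied in 4.4.1?** The section tends to write its exceptions out:

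- Radiological progression carries one: "unless the subject is considered to derive clinical benefit from the treatment by the investigator, is clinically stable", with Sponsor agreement and a pointer to 5.4.5. That clause does not attach to clinical progression.
- Tumor flare has its own line: "Tumor flare phenomenon, defined as local pain, irritation, or rash localized at sites of known or suspected tumor does not require treatment discontinuation".
- Non-permitted drugs are tied to 5.5.2, with room to consult: "in which the predefined consequence is withdrawal from study drug (Sponsor may be contacted to discuss whether trial treatment must be discontinued".

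The palliative-radiation item has nothing comparable.

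**4. Do the anticancer treatments named beside it conflict in the same way?** No. Chemotherapy is prohibited in 5.5.2. Surgery for tumor control or symptom management is ruled out in 5.5.1. Palliative radiation is the one treatment in the line with an express hold-and-resume rule.

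**5. What is the difference for one subject?** Inputs:

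- dosing every 2 weeks (5.4.1.1);
- the separate withdrawal rule in 4.4.1, "Dose delay which results in no AGEN2034 dosing for more than 6 weeks", read as the gap between doses, which is how 6.4.1.11 describes a delay;
- the course length in 5.4.1.1, "In both Phases, subjects will be treated for up to 24 months, regardless of dose delays, as long as the subject meets criteria";
- 30.4375 days per month (SAP 7.2).

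Longest hold under 5.5.1, with doses on their nominal days and the last dose at week 0:

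- Skip weeks 2 and 4, resume at week 6: gap = 6 weeks, not more than 6, so allowed.
- Skip weeks 2, 4 and 6, resume at week 8: gap = 8 weeks, over the limit.

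A hold can therefore skip at most 2 consecutive doses.

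Full planned course: 24 × 30.4375 / 14 = 730.5 / 14 = 52.2 two-week intervals. The literal 4.4.1 rule removes whatever part of that course remains when radiotherapy starts.

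**The case against.** The strongest counter-reading is that the item is not a free-standing trigger. It sits under clinical progression, and its neighbours are signs of progression. On that view, radiation prompted by progression leads to withdrawal, and 5.5.1 covers a narrower case of symptom relief. Taken literally, the list would also force withdrawal for an ECOG decline caused by an infection, which suggests that it was meant as evidence of progression. This may well be what the authors intended, but the text does not say so: one or more items suffice, and no section reconciles the two rules. If that is the intended meaning, the same short edit would state it.

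Several smaller points stand:

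- Chronic opiates appear in the same item, and 5.5.2 does not prohibit them, while 5.5.1 allows supportive care for symptoms. Palliative radiation is therefore not the only otherwise acceptable treatment in the line. It is the one with an explicit instruction to resume drug.
- The washout paragraph of 5.5.2 describes the 5.5.1 exemption as bone-directed, a limit that 5.5.1 does not contain.
- Section 4.4.1 is loosely drafted (tumor flare, a non-reason, sits among the withdrawal reasons), so its silence is weaker evidence than it would be in a tight text.
- The 52 intervals are the ceiling for a whole course, not the expected loss. A subject needing palliative radiation has usually used part of the course and may stop soon for other reasons.
- The SAP describes enrollment as having reached its final stage, so an amendment helps only subjects still on drug.

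These points limit the size of the problem. They do not remove the contradiction.

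**Conclusion.** The concern holds. For a subject without RECIST progression who receives palliative radiotherapy within the limits of 5.5.1, the two sections cannot both be followed. The conclusion rests on the plain wording that any one sub-item suffices and on the absence of any cross-reference between the sections.

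The number of subjects affected is unknown because the documents give no rate of on-study palliative radiotherapy. For one subject, the contrast is a pause of at most 2 skipped doses (nominal dosing days, 6-week limit counted between doses) against the loss of all remaining doses in a course of up to 24 months. No effect on the ORR conclusion is claimed. The rule governs whether a subject keeps receiving treatment and the remedy is very cheap, so it should be corrected.

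**What to change.** In Protocol 4.4.1, change the item to *palliative radiation therapy (other than that permitted in Section 5.5.1)* and tell sites by memo. Every other reason for withdrawal stays in force, including the remaining clinical-progression items and the 6-week dosing limit.

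Optionally, add one SAP sentence stating that radiotherapy given in line with 5.5.1 is not a new anti-cancer therapy for BOR, DOR and PFS (SAP 7.7.1, 7.7.3 and 7.7.9). The protocol already points that way: 5.5.1 treats it as concomitant care not aimed at tumor control, 4.4.1 lists it apart from new antineoplastic therapy, and 6.4.1.9.1 concerns new antineoplastic therapy begun after the last dose.

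The cost is one protocol phrase, one memo and, if wanted, one SAP sentence. No new data are needed.

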### 5.4.4.2. Treatment Delay

#### 5.4.4.2.1. *Criteria for Treatment Delay*

AGEN2034 administration should be delayed for the following:

- Any Grade  $\geq 2$  non-skin, drug-related AE with the following exceptions:
  - Do not delay treatment for Grade  $\geq 2$  Fatigue and laboratory abnormalities except for:
    - Delay dosing for Grade  $\geq 2$  serum creatinine (more than 1.5x baseline) toxicity
    - If a subject has a baseline AST, ALT, or total bilirubin that is within normal limits, delay dosing for drug-related Grade  $\geq 2$  toxicity;
- Any Grade  $\geq 3$  skin drug-related AE or suspected Stevens-Johnson syndrome (SJS) or toxic epidermal necrolysis (TEN)
- Any Grade  $\geq 3$  drug-related laboratory abnormality with the following exceptions for lymphopenia, AST, ALT, or total bilirubin:
  - Grade 3 lymphopenia does not require a dose delay.
  - If a subject has a baseline AST, ALT, or total bilirubin that is within normal limits, delay dosing for drug-related Grade  $\geq 2$  toxicity.
  - If a subject has baseline AST, ALT, or total bilirubin within the Grade 1 toxicity range, delay dosing for drug-related Grade  $\geq 3$  toxicity.
- Any AE, laboratory abnormality, or inter-current illness which, in the judgment of the investigator, warrants delaying the dose of study drug.

Subjects receiving AGEN2034 who have drug-related toxicities that meet the criteria for dose delay should have treatment delayed until retreatment criteria are met.

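### The 6-week withdrawal rule in Protocol 4.4.1 has no exception for endocrinopathies controlled on hormone replacement, which other provisions allow to continue

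*Protocol*

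**What the plan says.** Protocol 4.4.1 lists events for which a subject has to come off treatment; any single item is enough. One item is "Any Grade 2 or 3 drug-related toxicity that does not resolve in" 6 weeks or less. It has no exception and no cross-reference.

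A later item in the same list concerns Grade 3 non-skin events lasting more than 7 days. Nested under it is an exception: "Grade 3 drug-related endocrinopathies adequately controlled with only physiologic hormone replacement do not require discontinuation".

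Elsewhere in the Protocol:

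- Section 5.4.4.2.2 sets return to Grade 1 or baseline as the general condition for restarting drug. It then names endocrinopathies controlled by physiologic replacement among the exceptions, with no grade or time limit.
- Table 8 (Section 5.6.5) resumes drug once a symptomatic endocrinopathy improves, whether or not hormone replacement is in use.
- Section 5.5.2 permits replacement corticosteroid on study, giving prednisone 5 to 7.5 mg daily as the example.
- Section 4.4.1 also withdraws for a need for 10 or more "mg per day of prednisone (or equivalent) for" longer than 6 weeks, and for "Dose delay which results in no AGEN2034 dosing for more than 6 weeks".

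**The concern.** An endocrinopathy on stable replacement is controlled but not resolved. If it is still graded 2 or 3 after 6 weeks, the 6-week bullet requires withdrawal, while the resumption rule and Table 8 expect dosing to go on. No text ranks these provisions.

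What is at stake is first the subject's continued access to drug. Second is the consistency of planned safety outputs. SAP 7.6.2 tabulates treatment-emergent events leading to permanent discontinuation. It also reports the percentage leading to drug discontinuation within immune-mediated clusters, including hypothyroidism, hyperthyroidism, thyroiditis, pituitary-adrenal disorders and diabetes. Those percentages could vary with how a site reads 4.4.1 and not only with the drug's toxicity.

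The events are foreseeable. Protocol 1.1.3.2 counts endocrinopathies among the most common immune-mediated reactions to nivolumab, and Protocol 1.1.2.2 takes nivolumab's safety profile as the best guide to AGEN2034.

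**Working it through.** The plan states no figure on this point, so the main check compares provisions.

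**1. Result for a drug-related endocrinopathy controlled by replacement alone and still graded 2 or 3 after 6 weeks**

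| Provision | Grade 2 | Grade 3 |
|---|---|---|
| 4.4.1, 6-week bullet | Withdraw | Withdraw |
| 4.4.1, exception under the 7-day bullet | Not addressed | Discontinuation not required |
| 5.4.4.2.2 | May resume | May resume |
| Table 8 | Resume after improvement | Resume after improvement |

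The exception in the second row belongs to a different bullet. By layout it does not modify the 6-week bullet.

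**2. Could resolved mean controlled?** Section 4.4.1 does not define resolution. The nearest guide is 5.4.4.2.2, which ties it to Grade 1 or baseline and then lists controlled endocrinopathy as an exception. If control counted as resolution, that exception would be unnecessary.

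**3. Do the other withdrawal triggers already settle the case?** They do not.

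- Steroid trigger: replacement at 5 to 7.5 mg per day is below 10 mg per day, so it is not met.
- No-dosing trigger (4.4.1) and Sponsor consultation (6.4.1.11): both act on long gaps between doses. A subject who has resumed has no such gap.

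**4. Consistency with eligibility.** Exclusion criterion 9 does not count thyroxine, insulin or physiologic steroid replacement as systemic treatment, and it admits thyroid disease that needs no immunosuppression. A subject may therefore enter on thyroxine. One who develops drug-related hypothyroidism that stays Grade 2 on thyroxine would be withdrawn after 6 weeks.

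**5. Size per affected subject.** Inputs from the documents: one infusion every 2 weeks and a 24-month maximum that runs "subjects will be treated for up to 24 months, regardless of dose delays, as long as the subject meets criteria to remain on therapy" (Protocol 5.4.1.1); 30.4375 days per month (SAP 7.2). Assumptions: onset at week 6, 12 or 24, and treatment otherwise ending at 6, 12 or 24 months.

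- Withdrawal week = onset + 6 = 12, 18 or 30.
- End week = months × 30.4375 / 7 = 26.1, 52.2 or 104.4.
- Infusions forfeited = max(0, end week − withdrawal week) / 2.

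| Treatment would have ended at | Withdrawn week 12 | Withdrawn week 18 | Withdrawn week 30 |
|---|---|---|---|
| 6 months | 14.1/2 = 7.0 | 8.1/2 = 4.0 | 0 |
| 12 months | 40.2/2 = 20.1 | 34.2/2 = 17.1 | 22.2/2 = 11.1 |
| 24 months | 92.4/2 = 46.2 | 86.4/2 = 43.2 | 74.4/2 = 37.2 |

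The range is 0 to about 46. The upper end applies only to a subject who would have stayed on drug for the full 24 months.

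**6. Primary endpoint.** SAP 7.7.1 derives best overall response from all on-study assessments before a new anti-cancer therapy. Stopping drug does not by itself close that window.

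**The case against.** The strongest defence is that the 6-week bullet is a deliberate general cap, with the delay and resumption rules working inside it. The layout allows this, and several Grade 2 events fit it. Grade 2 fatigue and Grade 2 skin toxicity may be dosed through under 5.4.4.2, and a permission to dose meanwhile is not a permission to continue indefinitely. That much stands, and no conflict is claimed for those events. Controlled endocrinopathy differs because 4.4.1 itself says the Grade 3 form need not lead to discontinuation, and because Table 8 treats improvement on replacement as sufficient to resume.

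A second defence is that a specific clause governs a general one, so a careful site would continue treatment. This is reasonable at Grade 3. The Protocol does not state that principle, however, and the clause does not mention Grade 2. The defence supports a minor rating but does not remove the ambiguity.

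A reader might also infer that the bullet inverts the handling of lymphopenia: Grade 2 or 3 beyond 6 weeks is withdrawn, while "Grade 4 lymphopenia or leukopenia" is listed as not requiring discontinuation. The documents do not support this. Section 5.4.4.2.1 delays dosing for any Grade 3 or higher "drug-related laboratory abnormality with the following exceptions for lymphopenia, AST, ALT, or total bilirubin", and its lymphopenia exception covers Grade 3 only. Grade 4 is therefore held, can resume only at Grade 1 or baseline under 5.4.4.2.2, and is withdrawn under the no-dosing trigger after more than 6 weeks. A 6-week cap at Grades 2 and 3 is coherent with that, and exempting lymphopenia would be a clinical choice, not a correction.

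**Conclusion.** The concern holds for endocrinopathies adequately controlled with physiologic hormone replacement alone, and for no other event type. For these, the 6-week bullet read literally gives a result that contradicts 5.4.4.2.2 and Table 8, and at Grade 3 also contradicts another item in 4.4.1.

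The conclusion rests on the event being drug-related and still graded 2 or 3 after 6 weeks; the documents do not say how a controlled endocrinopathy is graded. They give no rate of such persistence, so the number of affected subjects cannot be derived. The 0 to 46 infusions per affected subject depends wholly on the assumed onset and end times.

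The consequence is for treatment continuation and the SAP 7.6.2 discontinuation summaries. It would go too far to infer a threat to the primary analysis, since response is assessed up to new anti-cancer therapy whether or not drug has stopped. Severity: minor.

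**What to change.** Add an exception to the 6-week bullet in Protocol 4.4.1 for Grade 2 or 3 endocrinopathies adequately controlled by physiologic hormone replacement alone, and cross-reference it in 5.4.4.2.2. Add no exemption for lymphopenia or other laboratory abnormalities.

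Safeguards stay in place: the investigator-judgment item in 4.4.1 still allows withdrawal where continuing poses a substantial risk, and so does the trigger of 10 mg or more of prednisone daily for over 6 weeks.

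The cost is one clause, one cross-reference and a clarification memo to sites. No new data collection is needed.
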